8.4 Pharmacogenomics (Whole Blood)

Subjects will have whole blood collected at baseline. Refer to *Study Manual* for collection, processing, and submission details.

Whole blood will be stored for possible future analysis of HLA type under the direction of [name] with the consent of the patient.

8.5 Viral Load

Plasma and urine samples will be collected at the following time points: baseline (prior to seroconversion dose on C1D1), C1D8, C1D15, prior to treatment on C1D22, C1D29, prior to treatment on C2D1, prior

to treatment on C3D1, prior to treatment on C4D1, and at 30-day off treatment follow up visit. Peritoneal fluid will be collected at baseline (prior to seroconversion dose on C1D1), prior to treatment on C2D1, prior to treatment on C4D1, and 30-day off treatment follow-up. If the subject comes off treatment mid cycle, take an additional plasma and peritoneal sample at the time of disease progression or off treatment.

Plasma, urine and peritoneal fluid will be collected, frozen and stored at the site (at -80) until such time as deemed appropriate for analysis. When ready for viral load analysis, plasma, urine and peritoneal fluid samples will be shipped to [name] lab at LSU. A quantitative primer will be used to detect HSV-1 DNA in plasma, urine, and peritoneal fluid samples via polymerase chain reaction (PCR).

8.6 Peritoneal Cytokine Levels

Peritoneal fluid will be collected at baseline (prior to seroconversion dose on C1D1), prior to treatment on C2D1, prior to treatment on C4D1, and 30-day off treatment follow-up. If the subject comes off treatment mid cycle, take an additional peritoneal fluid sample at the time of disease progression or off treatment.

These samples will be processed and stored by the Duke Immune Profiling Core under the direction of [name]. Supernatent will be transferred to the Duke Phase 1 Biomarker Laboratory under the direction of [name]. Aliquots from all samples will be retained by [name] for analysis, including but not limited to, IL1 β , IL2, IL4, IL5, IL6, sILR6R, sGP130, IL7, IL8, IL10, IL12, IL13, IL15, IL17A, IL17E, IL22, IL23, IFN γ , TGF β 1, and TGF β 2, but could include other markers that represent best science for this drug and involved signaling pathways. Remaining supernatent will be transferred to [name] lab at LSU for above mentioned viral load analysis via previously described PCR techniques.

8.7 Future Use of Patient Samples

Any remaining biological materials at the end of the study will be deidentified and deidentified samples may be retained for possible use in biomarker research with the consent of the patient. Remaining samples will be retained at the laboratory location of their analysis.

9.0 STATISTICAL ANALYSIS

9.1 General Analysis Considerations

Up to 30 subjects will be enrolled and treated. The intent to treat population is defined as all subjects who receive treatment with talimogene laherparepvec at the MTD.

The per protocol population is defined as all subjects who:

- Undergo treatment with talimogene laherparepvec
- Fulfill all inclusion and exclusion criteria
- Are evaluable for the primary efficacy criterion, TTP

The safety population consists of all the subjects who receive talimogene laherparepvec for whom safety data is available. All safety analyses will be carried out on this population.

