related toxicity (e.g. disease progression or inter-current illness) are considered non-evaluable for DLT. All subjects (in Dose Escalation and Dose Expansion) who are accrued, received study treatment but did not complete initial restaging due to reasons other than disease progression (e.g. inter-current illness) will be considered non-evaluable for efficacy.

Table 3.1 Proposed Dose Levels

Dose Level	No. Evaluable Subjects	TVEC IP, once every 2 weeks x 4 doses*
Dose Escalation		
1 (starting dose)	3-6	4×10^6
2	3-6	4×10^7
3	3-6	4×10^8
Dose Expansion		
Expanded Cohort	6	MTD

*All patients will receive an initial seroconversion dose of 4×10^6 PFU. The first dose at each of these Dose Levels will be administered 3 weeks (+3 days) after the initial seroconversion dose, and then be given every 2 weeks \pm 3 days for a total of 4 doses at each Dose Level (in addition to the initial seroconversion dose, which all patients will receive).

Using a standard '3+3' dose escalation design, there are up to three dose levels that may be explored. See Table 3.1 for the dosing scheme.

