5.3 Treatment Period

During the Treatment Period, subjects will receive an initial seroconversion dose of talimogene laherparepvec on Day 1 of Cycle 1. Three weeks (± 3 days) after the initial seroconversion dose, patients will receive talimogene laherparepvec at their designated dose level every 2 weeks (± 3 days) for up to four doses or until either: 1) the occurrence of unacceptable treatment-related toxicity; or 2) other reason(s) for subject discontinuation as described in [Section 5.7](#).

All subjects will have study procedures weekly during the first cycle, then Day 1 of each cycle. After the completion of the first cycle, laboratory assessments may be obtained up to 3 days prior to Day 1. If clinically indicated, additional visits and/or safety assessments may be warranted.

The following study procedures must be completed on Day 1 of each cycle:

- Physical examination
- Abdominal measurement
- Vital signs (q15 min x 1 hour and again after additional hour of observation)

- Weight
- Concomitant medications
- ECOG performance status
- Adverse event assessment
- CBC with differential (results from eligibility review on day -7 to -3 should be used for C1D1)
- Chemistries including LFTs (results from eligibility review on day -7 to -3 should be used for C1D1)
- Viral load (prior to treatment D1 of each cycle)
- Urine pregnancy test prior to each treatment (only for women of childbearing potential)
- Peritoneal Cytokines (prior to treatment on C2D1 and C4D1)
- Immune cells (prior to treatment on C2D1 and C4D1)
- Plasma (prior to treatment D1 of each cycle)

The following study procedures must be completed on **Days 8, 15 and 29 of Cycle 1:**

- Physical examination
- Vital signs and weight
- Concomitant medications
- ECOG performance status
- Adverse event assessment
- CBC with differential
- Chemistries including LFTs
- Viral load

The following study procedures must be completed **on Cycle 1 Day 22:**

- Physical examination
- Vital signs (q15 min x 1 hour and again after additional hour of observation)
- Weight
- ECOG performance status
- CBC with differential
- Chemistries including LFTs
- Viral load (prior to treatment)
- Plasma (prior to treatment)

The following study procedures must be completed **at C4D1 (+/-3 days):**

- Concomitant medications
- Adverse event assessments
- Peritoneal cytokines (prior to treatment)
- Immune cells (prior to treatment)
- Plasma
- Viral load (prior to treatment)

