9.1.4 Exploratory Endpoints

In addition to defining the MTD, the study will provide useful preliminary data concerning efficacy. Methods of assessing response will be specific to each individual patient as described in Section 5.6. In the subset of patients with radiographically measurable disease RECIST 1.1 criteria will be used.

Patients in the per protocol population will be classified as responder or non-responder and the proportion of patients exhibiting response at trial closure by any criteria will be estimated by the 90% confidence interval. Patients who experience a radiographic/tumor marker CR will undergo confirmatory laparoscopy.

Time to progression measured from study entry to documented progression of disease will be estimated by the method of Kaplan-Meier in the intent-to-treat population. Patients who withdraw from the trial prior to disease progression, are either lost to follow-up, die or begin alternative treatments prior to progression, will be censored at the date considered to be lost to follow-up, date of death, or the first day of alternative therapy.

For all efficacy endpoints, analyses will be performed overall and in the patients treated at the MTD. These analyses are primarily exploratory since the data will be from only a limited number of patients available for the study.

As a first approach to addressing our exploratory aim of evaluating changes in peritoneal cavity leukocyte populations after the treatment of peritoneal surface dissemination of gastrointestinal, fallopian tube, ovarian, and primary peritoneal cancers with talimogene laherparepvec, we will perform multi-color flow cytometry analysis on peritoneal lavage fluid from patients at baseline (prior to seroconversion dose on C1D1), prior to treatment on C2D1, and on C4D1. If the subject comes off treatment mid cycle, there will be an additional plasma sample at the time of disease progression or off treatment. Immune cells will be stained with fluorescent antibodies specific for markers of major leukocyte subsets as commonly performed by the [name] Lab.

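### The set labelled intent-to-treat requires receipt of the MTD, which can start about three weeks after Day 1, while TTP runs from an undefined study entry; Section 3.1 also contradicts itself on who is evaluable for efficacy

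*Combined protocol and SAP*

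**What the plan says.** Section 9.1 defines the main set by dose received: "The intent to treat population is defined as all subjects who receive treatment with talimogene laherparepvec at the MTD". Under Sections 3.1 and 3.3 every subject, whatever the cohort, receives 4×10^6 PFU on Cycle 1 Day 1 (C1D1). Cohort-level dosing comes later; the footnote to Table 3.1 says "The first dose at each of these Dose Levels will be administered 3 weeks (+3 days) after the initial seroconversion dose".

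Section 9.1.4 says that TTP, "measured from study entry to documented progression of disease will be estimated by the method of Kaplan-Meier in the intent-to-treat population". Section 3.1 defines enrolled (consent given) and accrued (consent and eligible), but no section defines study entry. Footnote 3 of Appendix C allows consent more than 28 days before C1D1.

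For response, Section 9.1.4 says "Patients in the per protocol population will be classified as responder or non-responder", and that "the proportion of patients exhibiting response at trial closure by any criteria will be estimated by the 90% confidence interval". One condition of the per-protocol set in Section 9.1 is that subjects "Are evaluable for the primary efficacy criterion, TTP". Section 3.1 has two statements on efficacy evaluability. Its Evaluable bullet includes every accrued subject given any study treatment. Its Non-evaluable bullet removes treated subjects who missed the initial restaging for a reason other than progression.

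Section 9.1.4 adds: "For all efficacy endpoints, analyses will be performed overall and in the patients treated at the MTD".

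**The concern.** An intent-to-treat set should be fixed at baseline. If the MTD is one of the two higher levels, membership here depends on something that happens about three weeks after the first dose. Anyone in the set has by definition stayed on treatment long enough to receive a cohort-level dose, yet their time is counted from an earlier point. Subjects who progress early and stop are missing from the part of the curve where their events would fall.

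The undefined origin is a second problem. Consent, accrual and C1D1 are all defensible readings, and moving from C1D1 to consent could add more than 28 days to a subject's TTP with no change in outcome.

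The third problem does not depend on which level becomes the MTD. A treated subject who misses restaging through intercurrent illness is evaluable under one sentence of Section 3.1 and non-evaluable under another. The per-protocol set rests on evaluability, and no separate rule for TTP evaluability is given, so the response denominator cannot be settled from the text.

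Two analysts following the plan could therefore report different n, TTP curves and response rates for the dose taken into expansion. With open-label data, the choice could be made after outcomes are known.

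**Working it through.** **1. The plan's own figure.** Section 9.1.3 gives n = 12 for the intent-to-treat set, with 90% precision of ±0.237 (two-sided) and 0.185 (one-sided). Both reproduce from the normal approximation at p = 0.5: sqrt(0.25/12) = 0.1443; 1.645 × 0.1443 = 0.237; 1.282 × 0.1443 = 0.185. The 12 matches 6 subjects at the MTD plus 6 in expansion (Sections 3.2 and 3.3).

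**2. Who leaves the set.** Under Section 7.1, a dose delayed by more than one week is treated as missed and the subject goes on to the next visit. Missing the Day 22 dose alone therefore does not exclude anyone. Only a subject who receives none of the up to four cohort-level doses is left out.

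**3. How many early progressors there could be.** The documents give no TTP median, so I assume exponential medians m of 60 to 183 days. The share progressing within d = 21 days of C1D1 is 1 − 2^(−d/m):
- m = 60: 1 − 2^(−21/60) = 0.215, or 2.6 of 12.
- m = 183: 1 − 2^(−21/183) = 0.077, or 0.9 of 12.

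Allowing three days either side (d = 18 to 24) widens the range to 0.8-2.9 of 12. This is an upper limit, because the first scheduled scan is at C4D14, which is Day 35 + 14 + 14 + 14 = 77. Earlier progression would have to be picked up from symptoms, markers or an unscheduled scan.

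**4. How many would be excluded.** Assume that 25% of progressions are documented when they occur, and that each one documented before the first cohort-level dose ends treatment. Then 0.25 × (0.066 to 0.242) = 1.6-6.1% are excluded, or 0.2-0.7 of 12.

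**5. Effect on the TTP median.** The remaining 75% are documented at scans on Days 77, 161, 245 and so on (84-day spacing). I compared the medians with and without the excluded subjects for each whole-day m from 60 to 183 (124 values). The mean shift is about 6 to 8 days, the range is 0 to 33, and the shift is zero for 78-80 of the 124. With 10% documented early, the mean shift is 2.3-3.1 days and it is zero for 105-107 of the 124.

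**6. Effect on the curve per subject.** If k early progressors are dropped from 12 and there is no earlier censoring, later Kaplan-Meier values are multiplied by 12/(12 − k): 1.09 for k = 1 and 1.20 for k = 2. For example, 6/12 = 0.50 becomes 6/11 = 0.55. If instead the subject who left before any cohort-level dose was progression-free, the value falls to 5/11 = 0.45.

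**7. Response denominator.** These are illustrative counts among 12 subjects at the MTD, with exact (Clopper-Pearson) 90% limits:
- All treated subjects count: 2/12 = 16.7% (3.0-43.8%). Two un-restaged non-responders removed: 2/10 = 20.0% (3.7-50.7%).
- All treated subjects count: 3/12 = 25.0% (7.2-52.7%). One un-restaged clinical responder removed: 2/11 = 18.2% (3.3-47.0%). This is possible because Section 5.7 lets symptom improvement count towards response.

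**The case against.** The strongest reply is that the intended set can be inferred. With n = 12 in Section 9.1.3, the phrase about receiving the MTD probably means being in the MTD cohort, and then no one is selected after baseline. This carries weight, but Section 9.1 speaks of receiving treatment, and Section 3.3 places dosing at the MTD three weeks after C1D1. An analyst applying the definition literally would not be wrong.

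An all-subject efficacy analysis also appears to be planned already. Section 9.1.2 contrasts overall with by dose level, and the same word in Section 9.1.4 most naturally means all dose levels. That stands as mitigation, although the plan does not say so or name the main TTP analysis.

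Finally, TTP and response are exploratory objectives (Section 2.3), and Section 9.1.1 limits the statistics to description. That stands too. Section 9.1 does call TTP the primary efficacy criterion, so readers may still give it weight.

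A reader might infer more than the documents support:
- **That early progressors are removed systematically and the median rises by the full 21 days.** This would need every progression before Day 22 to be documented and to end treatment. The first scheduled scan is at Day 77. The Synopsis ends treatment at progression, but Section 5.8 allows exceptions after radiographic progression.
- **That anyone who misses the Day 22 dose is lost.** Section 7.1 says otherwise.
- **That with an MTD of 4×10^6 PFU the set would take in all cohorts through their Day 1 dose.** The wording permits this, but n = 12 argues against it.

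**Conclusion.** The point holds as a defect of definition with a small expected effect on TTP. If the MTD is 4×10^7 or 4×10^8 PFU, the set labelled intent-to-treat depends on a post-baseline event, and its TTP origin is undefined whichever level is chosen. Dropping early progressors tends to lengthen TTP. The likely number is 0.2-0.7 of 12, with no change in the median for most assumed values. That rests on exponential TTP with a median of 60-183 days and 25% early documentation, none of which comes from the documents. The ceiling, if every early progression were documented and led to exclusion, is 0.8-2.9 of 12.

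The contradiction over efficacy evaluability is plain on the text and applies at any MTD. Its effect is a few percentage points on a response rate whose 90% interval is already about 40 points wide or more. Removing un-restaged subjects will usually raise the rate, but not always.

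No dose-escalation decision or safety analysis is affected. The definitions should be corrected before analysis because the repair is cheap.

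**What to change.** - **Efficacy set.** For TTP and response, define the MTD efficacy set as all subjects assigned to the MTD level who receive any talimogene laherparepvec, including the C1D1 dose. Do not call a set defined by dose received intent-to-treat.
- **Origin.** Define study entry for TTP as C1D1.
- **One evaluability rule.** Replace the two statements in Section 3.1. I suggest that all treated subjects stay in the response denominator, that un-restaged subjects count as non-responders unless they meet another stated response criterion, and that the restaged or per-protocol set is a sensitivity analysis. A response-evaluable set is another convention; the essential step is to choose one rule in advance.
- **Overall.** State in Section 9.1.4 that overall means all treated subjects across dose levels, and name the main TTP analysis.
- **Correlative estimates.** Keep a separate set of subjects who received the MTD for the viral-load, cytokine and immune-marker estimates in Section 9.1.3, so that they still describe that dose.
- **Dose window.** Sections 3.1 and 3.3 give +3 days for the first cohort-level dose, while Section 5.3 reads "Three weeks (± 3 days) after the initial seroconversion dose, patients will receive talimogene laherparepvec at their designated dose level". These passages must be reconciled, but the point does not turn on them.

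The cost is a few sentences and one or two extra tables. Section 5.4 already follows subjects for progression after treatment stops, so no new data are needed. TTP and response figures may look slightly less favourable.

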9.1.1 Statistical Methods

- The statistical analyses will be performed on the intent to treat, the per protocol, and safety populations.
- Statistical analyses will be only descriptive.
- Descriptive statistics will be provided according to the nature of variables
- Mean, standard deviation, minimum and maximum, median and quartiles will be provided for quantitative variables.
- Percent and frequencies will be provided for qualitative variables.
- Time to events will be illustrated with survival curves using the Kaplan-Meier method.
- Confidence intervals will be constructed from outcomes intent.

9.1.2 Primary Endpoint

The primary objective of the study is to define the safety and toxicity profile of talimogene laherparepvec in patients with peritoneal surface dissemination from gastrointestinal, fallopian tube, ovarian, or primary peritoneal tumors. The MTD across three dose levels will be determined as described in Table 3.1. The safety analyses will be performed on the safety population, as defined above. Incidence of adverse events occurring in 10% or more of patients will be summarized by Grade, overall and by dose level.

Adverse events will be described using the NCI CTCAE 5.0 criteria. Frequency and severity of adverse events according to the NCI CTCAE v 5.0 body system and severity criteria will be described. In addition, frequency of Grade 3 or 4 adverse events will be described separately. Causality will also be noted.

Laboratory assessments will also be described according to the NCI CTCAE criteria, with separate descriptions for Grade 3 or 4 laboratory abnormalities. Clinically significant laboratory abnormalities will be described as well. Serious adverse events will be summarized, including a causality assessment.

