dose, which all patients will receive). The length of the first cycle is 5 weeks and subsequent cycles are 2 weeks in duration.

In the Dose Escalation Cohort, there will be up to three dose levels explored in a standard '3+3' dose escalation design. Three subjects will be accrued at the starting dose level. If no DLTs are seen at that level, three subjects will be enrolled at the next dose level. If one of three subjects has a DLT at any dose level, an additional three subjects will be enrolled at that dose level. If one of six subjects experience DLT, then escalation may continue. If two or more subjects have DLT at any dose level, then that dose level will be considered to have unacceptable toxicity, the next lower dose level will have additional subjects enrolled. Up to six subjects will be enrolled at the maximum tolerated dose (MTD) before proceeding to the expanded cohort.

The Dose Expansion cohort will enroll subjects at the MTD and follow the treatment scheme described above.

Number of Subjects

The Dose Escalation Cohort will enroll 6 to 18 subjects.

The Dose Expansion Cohort will enroll 6 subjects.

A total of 12 to 24 evaluable subjects will be accrued to assess the safety and tolerability of intraperitoneal talimogene laherparepvec.

Estimated Length of Study Participation

Estimated duration of subject enrollment is 5 months.

Subjects may continue to receive study treatment until they receive up to 4 doses after the initial seroconversion dose, experience unacceptable drug-related toxicity, or disease progression. For subjects that discontinue study treatment with no documented disease progression and no subsequent anti-cancer treatment, they will be followed every 12 weeks or as clinically indicated with tumor evaluations until disease progression or start of new anti-cancer therapy is documented. All subjects will be followed for survival for 1 year after completing treatment.

Study Drug Regimen

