All patients will receive an initial seroconversion dose of intraperitoneal talimogene laherparepvec 4×10^6 PFU on Cycle 1 Day 1 to enable seroconversion as described in the currently approved treatment protocol for the treatment of cutaneous melanoma. Three weeks after the initial seroconversion dose, patients will receive talimogene laherparepvec at the dose level for the cohort for which they are enrolled every 2 weeks for up to 4 doses (in addition to the initial seroconversion dose, which all patients will receive). The length of the first cycle is 5 weeks and subsequent cycles are 2 weeks in duration.

In the Dose Escalation Cohort, three subjects will be enrolled at the starting dose of 4×10^6 PFU, and the dosing will continue in the standard '3+3' dose escalation scheme. If the starting dose is tolerated, enrollment will continue at 4×10^7 and 4×10^8 PFU. Once the MTD is determined, six subjects will be enrolled to the Dose Expansion Cohort at the MTD. All subjects will be dosed with talimogene laherparepvec IP once every 2 weeks for up to 4 doses (in addition to the initial seroconversion dose, which all patients will receive).

Study Assessments

Safety: Toxicity and safety assessments will be performed weekly during the 5 weeks, then every 2 weeks for up to 4 treatment visits. These assessments will include vital signs, ECOG performance status, medical history, physical examination, complete blood count (CBC), biochemistry, creatinine, AST, ALT, and bilirubin. Toxicities will be recorded using National Cancer Institute Common Terminology Criteria for Adverse Events (NCI-CTCAE) version 5.0. General symptom management and supportive care will be provided as clinically indicated to ensure optimal patient care. After discontinuation of study treatment, subjects will have toxicity and safety assessments 30 days after last dose of study drug.

Tumor Assessments

Restaging scans and blood tumor markers will be repeated at the end of cycle 4, after receipt of the fifth dose of study drug. Tumor response will be assessed using treating physician's discretion, based on a composite of RECIST 1.1 measurements, blood tumor markers (CEA or CA-125), measurements of abdominal girth, and/or clinical response.

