10.1 Adverse Events

An adverse event (AE) is defined as any untoward medical occurrence in a patient or clinical investigation subject administered a pharmaceutical product and which does not necessarily have to have a causal relationship with this treatment. An adverse event can therefore be any unfavorable and unintended sign (including an abnormal laboratory finding, for example), symptom, or disease temporally associated with the use of a medicinal product or protocol-specified procedure, whether or not considered related to the medicinal product or protocol-specified procedure. Any worsening (i.e., any clinically significant adverse change in frequency and/or intensity) of a preexisting condition that is temporally associated with the use of the supporting company product(s), is also an AE.

Changes resulting from normal growth and development that do not vary significantly in frequency or severity from expected levels are not to be considered AEs. Examples of this may include, but are not limited to, teething, typical crying in infants and children and onset of menses or menopause occurring at a physiologically appropriate time.

Supporting company product includes any pharmaceutical product, biological product, device, diagnostic agent or protocol-specified procedure, whether investigational (including placebo or active comparator medication) or marketed, manufactured by, licensed by, provided by or distributed by the supporting company for human use.

AEs may occur during the course of the use of supporting company product(s) in clinical trials or within the follow-up period specified by the protocol, or prescribed in clinical practice, from overdose (whether accidental or intentional), from abuse and from withdrawal.

Progression of the cancer under study is not considered an AE unless it is considered to be drug related by the Investigator.

AEs will be documented from the date of first dose of study drug through 30 days after the last dose of study drug. All Grade 2-5 AEs as well as special reporting circumstances, such as exposure via a parent during pregnancy or breast-feeding, overdose, medication error, misuse, abuse, off-label use or occupational exposure must be recorded on the CRF.

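### The by-dose-level adverse event table counts events from Day 1, although every subject is on the same 4×10^6 PFU dose until about Day 22; a supplementary split at the first cohort-level dose would sharpen it

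*Combined protocol and SAP*

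**What the plan says.** **Dosing.** The synopsis (Study Drug Regimen) states: "All patients will receive an initial seroconversion dose of intraperitoneal talimogene laherparepvec 4×10^6 PFU on Cycle 1 Day 1 to enable seroconversion". The Table 3.1 footnote in section 3.1 adds: "The first dose at each of these Dose Levels will be administered 3 weeks (+3 days) after the initial seroconversion dose". At level 1, "three subjects will be enrolled at the starting dose of 4×10^6 PFU", the same as the common dose. For the higher levels: "If the starting dose is tolerated, enrollment will continue at 4×10^7 and 4×10^8 PFU". On timing: "The length of the first cycle is 5 weeks and subsequent cycles are 2 weeks in duration".

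**Collection.** Section 10.1: "AEs will be documented from the date of first dose of study drug through 30 days after the last dose of study drug". The safety population in section 9.1 is everyone who receives the drug and has safety data, so it includes a subject who stops before the first cohort-level dose.

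**Tabulation.** Section 9.1.2: "Incidence of adverse events occurring in 10% or more of patients will be summarized by Grade, overall and by dose level". The same paragraph ties the levels to Table 3.1: "The MTD across three dose levels will be determined as described in Table 3.1". The seroconversion dose is not a level in that table.

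**Silent.** No section splits adverse events by period or by dose at onset, defines *dose level* for the table, or says where a subject who stops before Day 22 is counted. Section 10.2 asks for the dose level at the time of the event, but only in SAE reports.

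**The concern.** The primary objective is the toxicity profile of the intraperitoneal drug, and this table is where a reader will look for how toxicity changes with dose. If *dose level* means the Table 3.1 cohort, a Day 2 fever in a level 3 subject is listed under 4×10^8 PFU although the subject has received only 4×10^6 PFU. Every row then carries a background from the same first dose. That background raises all rows and makes the levels look more alike than they are after cohort-level dosing. At level 1 the two doses are equal, so a wrong dose label can arise only at levels 2 and 3. A subject who stops before Day 22 also enters the denominator of a level never received.

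**Working it through.** The plan states no figure for this point, so there is none to reproduce.

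**1. Calendar.** Cycle 1 lasts 35 days and cycles 2 to 4 last 14 days each. Doses fall on Days 1, 22, 36, 50 and 64. Collection ends nominally on Day 64 + 30 = Day 94.
- After all five doses, the common-dose period is 21 of 93 elapsed days (23%).
- After two doses only, collection ends on Day 22 + 30 = Day 52, and the share is 21 of 51 (41%).

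The 21 days are nominal. Section 3.1 allows the first cohort-level dose up to 3 days late, while section 5.3 allows 3 days either way. These passages must be reconciled, but a split on the actual dosing date does not depend on which holds.

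**2. Size of the wrong label.** 4×10^7 / 4×10^6 = 10 at level 2; 4×10^8 / 4×10^6 = 100 at level 3.

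**3. Dilution.** Let p0 be the chance of a given event before the first cohort-level dose, equal at all levels, and p the chance from that dose on, taken as independent. The unsplit table shows

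1 − (1 − p0)(1 − p).

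The difference between two levels is therefore (1 − p0) × (p_high − p_low). It shrinks but keeps its sign. The documents give neither p0 nor p for intraperitoneal use. Both are assumptions here, with p = 10% at level 1 and 40% at level 3:

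| p0 | Level 1 shown | Level 3 shown | Difference | Ratio |
|---|---|---|---|---|
| 0 | 10% | 40% | 30 points | 4.0 |
| 0.05 | 14.5% | 43% | 28.5 | 3.0 |
| 0.10 | 19% | 46% | 27 | 2.4 |
| 0.20 | 28% | 52% | 24 | 1.9 |

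For example, at p0 = 0.10: 1 − 0.9 × 0.9 = 0.19 and 1 − 0.9 × 0.6 = 0.46.

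**4. How many level 3 entries rest on the first dose alone.** The share is p0(1 − p) divided by the incidence shown. At p0 = 0.10 it is 0.06 / 0.46 = 13%; at 0.05 it is 7%; at 0.20 it is 23%.

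**5. Small cohorts.** At p0 = 0.10, the chance that at least one subject has such an event in the common-dose period is 1 − 0.9^3 = 0.27 in a cohort of 3 and 1 − 0.9^6 = 0.47 in a cohort of 6. One such subject moves the row by up to 33 or 17 points.

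**6. What pooling offers.** As an illustration, 10 of 24 subjects with an event in the pooled first phase (24 is the upper planned number in the synopsis) has an exact 95% interval of 22% to 63%. A single level with 3 of 6 has 12% to 88%.

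**The case against.** **The plan does not say *assigned*.** This stands. Section 9.1.2 says only by dose level, and the SAE form uses the term for the time of the event. The link to Table 3.1 makes the cohort reading the natural one, but the documents do not settle it. The plan is silent rather than shown to be wrong.

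**A table by cohort is legitimate.** This also stands. Every subject gets the common dose and then up to four cohort-level doses, and the expansion cohort follows the same sequence. All events under a cohort describe that regimen. A reader might infer that the table overstates toxicity at levels 2 and 3; that is true only if the target is the cohort-level dose alone.

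**The effect may be small.** A reader might take p0 from the 42.8% pyrexia in Table 1.2.1.3. The table would then show 48.5% versus 65.7%, 17 points instead of 30. The documents do not support that as an estimate: it is an any-grade rate over a whole course of intralesional treatment, not a rate after one intraperitoneal dose. That row has no Grade 3-4 events, and section 10.1 requires only Grade 2-5 events on the CRF. It is at most an upper illustration. With 6 subjects per level, the standard error of a 10% versus 40% difference is √(0.09/6 + 0.24/6) = 0.23, so the dilution in the table above, and even this upper illustration, is smaller than sampling error.

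**No decision rests on the table.** Correct. Analyses are descriptive only (section 9.1.1), and the MTD comes from the DLT rules in section 3.2. Description is nevertheless the primary deliverable, so the dose attached to an event should be clear. Noting causality does not supply it, because relatedness is to the drug and not to a particular dose.

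**Conclusion.** The point holds as a worthwhile improvement to the primary description. On the natural reading of section 9.1.2, events from the common 4×10^6 PFU period appear under levels 2 and 3, and subjects who stop before about Day 22 appear under a level they never received. Seen as toxicity by dose, between-level differences are pulled toward zero by the factor (1 − p0): a loss of 1.5 to 6 points out of 30 for p0 from 0.05 to 0.20. This rests on assumed incidences, on p0 being equal across levels, and on independence of the two periods.

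Three stronger inferences are not supported. The order of the levels is not reversed. The MTD is not affected through this table. The first-dose information is not lost, because section 11.5 keeps onset dates in source notes and section 6.1 keeps drug-use records, so the split can be produced; the plan just does not commit to it.

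**What to change.** In section 9.1.2, keep the by-cohort and overall tables and label them whole-regimen. Add a supplementary table split by onset date:

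- **(a)** Day 1 until just before the first cohort-level dose: all treated subjects pooled at 4×10^6 PFU.
- **(b)** From the first cohort-level dose to 30 days after the last dose: by level received, with only subjects who received that level in the denominator.

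Count subjects who never receive a cohort-level dose in (a) and in the overall column. Count an event that starts in (a) and worsens in grade after the first cohort-level dose as new in (b).

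**Cost.** One extra table and a few lines of wording, with no change to dosing, visits or sample size. The documents do not say that the CRF carries the onset date; if it does not, one field is needed.

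**Limits to state with the table.** Late effects of the first dose can still fall in (b). Phase (a) is a single first exposure and (b) up to four repeat exposures, so the two phases differ in number and order of exposures and should not be compared as a pure dose effect. At level 1 they even share the same dose.
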